Whether albuminuria (as measured by the UMACR) is a good surrogate marker for progression of CKD in DM remains in question. There is a need for biomarkers that can detect kidney disease in earlier stages than UMACR and can reliably predict the progression of CKD. Analysis of biomarkers specific of tubulointerstitial kidney injury, the common pathway of progressive kidney disease will give us insight into the potential of such a surrogate marker of CKD. The presence of free light chains in the urine samples of patients with diabetes may be an indication of diabetic kidney disease if UMACR < 30. The effect of renoprotective drugs on UFCs warrants to be documented to follow these patients with CKD and thus explore the potential of UFC as a marker of kidney disease.

Supporting data

We hypothesized that urinary polyclonal free light chain excretion is elevated in early diabetic kidney as compared to controls and that urinary polyclonal free light chains excretion is elevated in early diabetic nephropathy before GFR declines. The objective was to investigate the excretion of urinary free light chains (UFC) in men and women, with and without DM, with a body mass index ≤ 27 or ≥ 30 . It was a cross-sectional study, with males and females between the ages of 18 and 70. Urine κ and λ FLC concentrations were measured by nephelometry, on a Dade-Behring BN™ II Analyzer using a particle-enhanced, high-specificity, homogenous immunoassay. In our study(20), there were three groups; controls (group I), obese without DM (group II), and obese with DM and HTN (group III). In group III, the mean HbA1c was $7.4 \pm 1.3\%$. See table 1 for the results.

Table 1: Results of the UFCs and UMACR

	I-Healthy Controls	II-Obese without DM	III- Obese with DM and HTN
N	10	40	30
Females	5	20	15
Age (years)	37.0 ± 10.5	45.7 ± 11.6	57.3 ± 7.0
BMI	22.5 ± 2.8	38.2 ± 7.5	41.6 ± 6.9
S. Creatinine (mg/dL)	0.79 ± 0.2	0.9 ± 0.3	0.9 ± 0.9
UMACR (mg/g)	9.2 ± 7.54	23.7 ± 61.6	27.2 ± 70.6
Urine Kappa (mg/L) ^{†*}	14.7 ± 11.1	34.0 ± 63.7	51.0 ± 71.8
Urine Kappa/Cr (mg/L) ^{†*}	0.01 ± 0.01	0.03 ± 0.06	0.04 ± 0.03
Urine Lambda (mg/L) [†]	5.8 ± 14.0	2.3 ± 3.9	8.7 ± 16.5
Urine Lambda/Cr (mg/L)	0.002 ± 0.003	0.002 ± 0.003	0.006 ± 0.013
Urine Kappa + Lambda (mg/L) [†]	20.4 ± 15.1	36.3 ± 66.9	59.7 ± 76.9
Urine Kappa + Lambda/Cr (mg/L) [†]	0.01 ± 0.01	0.02 ± 0.07	0.04 ± 0.04

UMACR= urine microalbumin creatinine ratio

† = $P < 0.05$ between groups I and III

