- 4- The urine free light chains: creatinine ratio as well as the urine microalbumin: creatinine ratio will be calculated and analyzed.

Analysis

Power and sample size

We plan to recruit 150 patients. Assumptions are: power = 0.8; alpha = 0.05, with 30% reduction in mean response being taken as significant. There is no data on the correlation of pre and post measures. We have set the correlation to 0.7 as Hutchison et al have demonstrated the correlation between urinary kappa and lambda light chains to be 0.88 with UMACR(7). The standard deviation from our data were \pm 72 mg/L for urinary kappa light chains and \pm 17 mg/L for urinary lambda chains in patients with DM and HTN. Assuming similar standard deviations in our sample for the proposed study, the sample size of 150 will allow us 80% power to detect a correlation coefficient of 0.7 between two normally distributed numerical variables when type I error is 5%.

Statistical analysis

Summary statistics such as mean, standard deviations, ranges, and percentiles of numerical variables will be given. Plots and goodness-of-fit tests will be generated to examine the distributions of the variables. Data will be log-transformed to normalized variables when necessary. If transformations do not resolve serious distribution problems, then nonparametric techniques will be considered as alternatives to parametric techniques. Outliers and influential points will be identified and examined.

Prevalence of incidence of interests will also be provided. Bar-plots and pie-charts will be produced for visual illustrations. Two-sample t-tests will be used to detect differences in numerical outcomes between groups, and chi-square tests will be employed to compare the frequencies of categorical outcomes. Linear or logistic regression models will be fitted to examine effects of covariates. Stepwise model selection methods will be used to identify for potential risk factors or prognostic variables. Residual analysis will be followed to validate the assumptions. All analyses will be performed using SAS version 9.1. Pearson or Spearman's correlation coefficients will be estimated between cystatin C and NGAL and traditional markers (blood pressure, lipids, UMACR, etc.) and UFCs.

This data will be presented in the form of poster(s) at scientific meeting(s) and used for peer reviewed publications and future grant applications.

Subject recruitment and safety

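### The power paragraph uses SDs of raw light-chain concentrations while the Methodology analyses creatinine ratios; no measure or scale is fixed, and the single 80% fits no marker in a two-sided untransformed test

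*Combined protocol and SAP*

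**What the plan says.** Under Analysis, Power and sample size, the plan states "We plan to recruit 150 patients" and "Assumptions are: power = 0.8; alpha = 0.05", "with 30% reduction in mean response being taken as significant". On the pre-post correlation, for which it says it has no data, it states "We have set the correlation to 0.7". Its variability inputs are given as "The standard deviation from our data were \pm 72 mg/L for urinary kappa light chains and \pm 17 mg/L for urinary lambda chains". The closing sentence attaches the 80% power to detecting a correlation coefficient of 0.7.

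Methodology item 4, just before that section, says: "The urine free light chains: creatinine ratio as well as the urine microalbumin: creatinine ratio will be calculated and analyzed". Aims 1 and 2, in the Specific Aims page and again in the Introduction, refer to the concentration of kappa and lambda chains, alongside UMACR. Neither light-chain measure is named as primary.

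Table 1 (Supporting data) reports both forms for the same 30 patients with diabetes and hypertension (group III, the last column). The ratio rows are "Urine Kappa/Cr (mg/L) ^{†*} 0.01 ± 0.01 0.03 ± 0.06 0.04 ± 0.03" and "Urine Lambda/Cr (mg/L) 0.002 ± 0.003 0.002 ± 0.003 0.006 ± 0.013".

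The Statistical analysis section allows log transformation when necessary and nonparametric methods as a fallback. It gives neither the sidedness of the tests nor the scale of the main pre-post comparison.

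**The concern.** For a percentage reduction in a mean, power depends on SD divided by mean (CV). That quantity differs between raw concentrations and creatinine ratios, and between kappa, lambda and UMACR. The plan enters SDs for one form of the light-chain measure, promises analysis of another, and prints one power figure for all markers.

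The study is meant to compare the response of light chains with that of UMACR and to support a grant application. A non-significant lambda or UMACR result could be read as no drug effect with 80% power behind it. A significant kappa/Cr beside a non-significant UMACR could be read as light chains being the more responsive marker, when a difference in spread alone can produce that pattern.

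**Working it through.** **Inputs.** N = 150, alpha 0.05, a 30% reduction and correlation r = 0.7 come from the power paragraph. Group III means and SDs come from Table 1. The plan's 72 and 17 mg/L are Table 1's 71.8 and 16.5 mg/L for raw kappa and lambda, rounded up. The plan names no test for the 30% reduction; a paired pre-post t-test is the natural reading.

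**Formula.** SD of the difference = SD × √(2(1 − 0.7)) = SD × √0.6. Standardised effect d = 0.30 × mean / (SD × √0.6) = 0.387 / CV. Power is from the noncentral t with 149 degrees of freedom.

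**The plan's own figure.** Raw lambda with SD 16.5 and a one-sided alpha of 0.05 gives n = (1.645 + 0.842)² × 1.897² × 0.6 / 0.30² ≈ 149 (150 with the t-distribution), and power 80.1% at N = 150. No other variant tried with the Table 1 point values reproduces 150. With the stated SD of 17, n is 159 one-sided and 202 two-sided. Raw kappa needs 84 and 107. The closing sentence does not reproduce either: testing r = 0.7 against zero by Fisher's z needs ((1.96 + 0.842) / 0.867)² + 3 ≈ 14 patients and involves no SD.

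**Power at N = 150, untransformed.**

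| Marker | Mean / SD | CV | d | Two-sided | One-sided |
|---|---|---|---|---|---|
| Raw kappa | 51.0 / 72 | 1.41 | 0.274 | 91.6% | 95.5% |
| Raw lambda, SD 17 | 8.7 / 17 | 1.95 | 0.198 | 67.4% | 78.0% |
| Raw lambda, SD 16.5 | 8.7 / 16.5 | 1.90 | 0.204 | 70.0% | 80.1% |
| Kappa/Cr | 0.04 / 0.03 | 0.75 | 0.516 | >99.9% | >99.9% |
| Lambda/Cr | 0.006 / 0.013 | 2.17 | 0.179 | 58.5% | 70.3% |
| UMACR | 27.2 / 70.6 | 2.60 | 0.149 | 44.3% | 56.9% |

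**Detectable reduction**, 80% power, two-sided: (1.96 + 0.842) / √150 × √0.6 × CV = 17.7% × CV. This gives 25% for raw kappa, 34-35% for raw lambda, 13% for kappa/Cr, 38% for lambda/Cr and 46% for UMACR.

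**Rounding in Table 1**, two-sided. Kappa/Cr at its worst (0.035 / 0.035) has 99.7%. Lambda/Cr runs from 48.4% (0.0055 / 0.0135) to 68.8% (0.0065 / 0.0125). That range includes the 67.4% for raw lambda with the plan's SD.

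**Correlation.** Lambda/Cr would match raw lambda if its own pre-post correlation were 1 − 0.3 × (1.954 / 2.167)² ≈ 0.76 (SD 17), or 0.77 (SD 16.5).

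**Log scale.** Under a lognormal approximation σ = √ln(1 + CV²) and d = −ln(0.7) / (σ√0.6) = 0.460 / σ, taking r = 0.7 on the log scale. Two-sided power is over 99.9% for raw kappa and kappa/Cr, 99.4% for raw lambda (SD 17), 98.9% for lambda/Cr and 97.5% for UMACR.

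**Reliability of the ratio rows.** They carry one or two significant digits and are labelled mg/L. In group II, kappa/Cr is 0.03 and lambda/Cr 0.002, but their sum is printed as 0.02. Even at the rounding limits the parts add to at least 0.025 + 0.0015 = 0.0265, while the printed sum is at most 0.025.

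**The case against.** The aims name concentrations, and item 4 adds ratios without saying that they replace them. The raw SDs therefore belong to a variable the study does intend to report. This stands: the fault is that the plan fixes no primary measure and does not power the ratio, not that it used an irrelevant variable.

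A reader might infer that moving to ratios shifts power in opposite directions, up for kappa and down for lambda. Only the kappa half is supported. For lambda the rounding range overlaps the raw figure, the CVs come from 30 patients, and a modestly higher correlation would cancel the loss.

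A reader might also blame the creatinine mismatch for the whole shortfall. Raw lambda with the plan's SD is already 12.6 points below 80% (80 − 67.4), which is more than half of the 21.5 points for lambda/Cr (80 − 58.5). UMACR is a ratio on any reading, so its low power is an omission from the paragraph and not a scale mismatch.

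The strongest objection is that a positive variable with an SD about twice its mean would probably be log-transformed, and power is then ample. This limits the consequence and rules out concluding that 150 patients are too few. It does not rescue the printed figure, because 80% is then wrong in the other direction and the plan leaves the choice of scale open.

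A one-sided test would bring raw lambda to 78-80%. The plan does not state one, and lambda/Cr and UMACR would still be at about 70% and 57%.

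**Conclusion.** The concern holds as a mismatch of inputs and an unspecified target. In a two-sided untransformed paired analysis the true figures run from about 44% to over 99%. The plan's 80% is recovered only for raw lambda, with the unrounded SD and a one-sided alpha that the plan does not state. On that scale a true 30% fall would be missed about 4 times in 10 for lambda/Cr and between 5 and 6 times in 10 for UMACR.

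These figures rest on r = 0.7 for every marker, group III spreads carrying over to the new sample, all 150 patients contributing both measurements, and untransformed analysis. The kappa/Cr result survives rounding. The documents do not establish that lambda/Cr is worse powered than raw lambda, or that N = 150 is inadequate.

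**What to change.** - Name the primary light-chain measure. The creatinine ratio matches item 4 and puts it on the same footing as UMACR. State the analysis scale, untransformed or log.
- Recompute the mean and SD, or the SD of the log ratio, for that measure and for UMACR from the pilot's patient-level data. The printed Table 1 ratio rows are too coarse and not internally consistent enough to serve as inputs.
- Keep N = 150. Replace the 80% statement, including the sentence on detecting a correlation of 0.7, with the power or detectable reduction for kappa, lambda and UMACR from a paired pre-post test of stated sidedness.
- Say which markers fall below 80%, and that a non-significant result for those is not evidence of no effect.

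The cost is one rewritten paragraph and a short reanalysis of the team's own pilot data, with no extra patients or samples. The downside is a less favourable stated power for lambda and UMACR if the data are analysed untransformed.

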Our **hypothesis** is that UFLCs are increased in patients with DM with and without nephropathy, and that treatment with Ace Inh and/or ARB will decrease UFLCs in these patients. Additionally, we will explore the change in other low molecular weight proteins [cystatin C, and NGAL in response to treatment with Ace Inh and ARB. We propose to test the hypothesis via the following specific aims:

Specific Aims:

- 1- We will determine the concentration of UFLCs (kappa and lambda) and UMACR in patients with DM with eGFR > 30 min/ml not on Ace Inh or ARB treatment.
- 2- We will determine the concentration of UFLCs (kappa and lambda) and UMACR in patients with DM with eGFR > 30 min/ml after treatment with Ace Inh and/or ARB for three months.
- 3- **Exploratory aim:** We will determine the concentration of urinary cystatin C and NGAL before and after treatment in the above patients to assess their response to Ace Inh and/or ARB class of drugs.

The **short term goal** of this study is to collect preliminary data on the effect that treatment with Ace Inh and ARB class of drugs have on UFLCs in comparison to UMACR. This data will be used to apply for funding for a longitudinal study to assess the effect of continuous treatment with Ace Inh and ARB on the levels of UFLCs in comparison to UMACR. The **long term goal** is to assess and compare UFLCs as a marker of kidney damage that can be used to diagnosis kidney disease earlier than UMACR; and if UFLCs can be used for prognosis and better prediction of progression to CKD.

Project Description - Introduction

Diabetes mellitus and kidney disease

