* = Trend toward significance between groups I and II [(free Kappa, $P = 0.07$), Kappa/Cr, $P = 0.08$)]

Results suggest excretion of urinary polyclonal free light chains is increased in obese subjects with DM and hypertension as compared to normal controls.

Limitations of this data include the cross-sectional design and use of Ace Inh and/or ARB class of drugs by 75% of the subjects in groups II and III. Therefore, the effect of Ace Inh and/or ARBs on the mean change of UFCs as compared to UMACR could not be assessed.

Approach

The proposed research project is aimed at studying the effect of anti-hypertensive medications on UFCs as compared to UMACR. We will recruit subjects with CKD stages I, II, and III. This will allow us to have a direct comparison between the two variables (UFCs and UMACR) across the above three stages of CKD, excluding stages IV and V. The reason for excluding patients with stages IV and V is that decreased clearance of the UFCs will confound the results.

Inclusion Criteria:

- 1- Men and women with DM, type 1 or type 2.
- 2- Age 18- 75
- 3- Estimated glomerular filtration rate (eGFR) > 30 ml/min
- 4- Hypertension
- 5- Use of Ace Inh and ARB for control of blood pressure who are willing to be placed on alternate drug(s) in the washout period for blood pressure control.

[figure not shown]
Exclusion Criteria:

- 1- Pregnancy
- 2- Patients with chronic kidney disease stage with eGFR ≤ 30 ml/min (CKD stage IV and V)
- 3- Nephrotic range proteinuria (urinary protein > 3.5 gm/day)
- 4- History or renal transplantation
- 5- History of multiple myeloma
- 6- Known history of hypersensitivity reaction or intolerance to Ace Inh or ARB, Amlodipine, Terazosin, Hydrochlorothiazide, and/or Hydralazine.

Research Design

This is a prospective, interventional study involving patients with either type I or type 2 DM and hypertension, which will be recruited from the outpatient clinics and the Tulane volunteer registry. Patients who meet the inclusion criteria on evaluation of blood work in the last 90 days of the visit will then undergo screening.

Information from the most recent laboratory data will be collected. There will be no genetic testing. The study is designed to include patients with and without diabetic nephropathy. All pertinent medications will be recorded as this information will be very important in interpreting the results of the data analyses. Below is a schematic representation of the visit schedule.

Washout period

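### The power statement concerns detecting a correlation of 0.7, not the 30% fall in light chains; against zero its 80% is wrong, and power for the fall is never given

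*Combined protocol and SAP*

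**What the plan says.** The hypothesis on the Specific aims page is directional and within patient: "treatment with Ace Inh and/or ARB will decrease UFLCs in these patients".

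The Power and sample size section opens with "We plan to recruit 150 patients". It then sets power 0.8 and alpha 0.05, "with 30% reduction in mean response being taken as significant". On the pre/post correlation it concedes: "There is no data on the correlation of pre and post measures". It nevertheless adopts 0.7, citing a published study that found "the correlation between urinary kappa and lambda light chains to be 0.88 with UMACR". It takes SDs of 72 mg/L (kappa) and 17 mg/L (lambda) from the team's earlier diabetic, hypertensive group. It concludes that "the sample size of 150 will allow us 80% power to detect a correlation coefficient of 0.7 between two normally distributed numerical variables", at 5% type I error.

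The section gives no baseline mean, null value for the correlation, sidedness, scale or allowance for missing follow-up samples. The Statistical analysis section leaves the scale open ("Data will be log-transformed to normalized variables when necessary"), and the only t-test it names is a two-sample test between groups.

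**The concern.** The inputs and the conclusion belong to different calculations. A 30% reduction, an SD and a pre/post correlation are what a paired comparison of means needs. Power to detect a correlation depends on N, alpha, the true correlation and the null. The 0.7 enters as an assumed nuisance value and returns as the effect to be detected.

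The basis for 0.7 is also off target. A correlation between light chains and UMACR describes agreement between different markers. It says nothing about how closely one marker tracks itself over three months.

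At stake is the only stated link between 150 patients and 80% power. As written, a reader cannot tell what power the study has for its own hypothesis. The results are meant to support a grant application for a larger study, so the statement may be carried forward.

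**Working it through.** **Inputs.** From Power and sample size: N = 150, alpha 5%, target power 80%, 30% reduction, correlation 0.7, SD 72 (kappa) and 17 (lambda) mg/L. From Table 1, group III: kappa 51.0 ± 71.8, lambda 8.7 ± 16.5 mg/L. The means appear only in Table 1.

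**1. The stated figure: correlation 0.7, N = 150 (Fisher z, two-sided 5%).**

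- atanh(0.7) = 0.8673. Against zero the signal is 0.8673 × √147 = 10.5, compared with a critical value of 1.96, so power exceeds 99.9%. The stated 80% is not reproduced.
- N for 80% power: ((1.960 + 0.842)/0.8673)² + 3 = 13.4, so 14 patients.
- Correlation detectable with 80% power at N = 150: tanh(2.802/√147) = tanh(0.2311) = 0.227.
- Nulls that would give 80%: tanh(0.8673 − 0.2311) = 0.562 and tanh(0.8673 + 0.2311) = 0.800.

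**2. Power for the 30% reduction, raw scale.** Paired t-test (noncentral t), equal SD before and after, SD of change = SD × √(2(1 − ρ)), 150 complete pairs.

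- Kappa: difference 0.3 × 51.0 = 15.3; at ρ = 0.7 the SD of change is 72 × √0.6 = 55.8.
- Lambda: difference 0.3 × 8.7 = 2.61; at ρ = 0.7 the SD of change is 17 × √0.6 = 13.2.

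| Setting (raw scale) | Kappa: power (N for 80%) | Lambda: power (N for 80%) |
|---|---|---|
| Two-sided, ρ 0.7 | 92% (107) | 67% (202) |
| Two-sided, ρ 0.5 | 73% (176) | 46% (335) |
| Two-sided, ρ 0.3 | 59% (246) | 35% (469) |
| One-sided, ρ 0.7 | 96% (84) | 78% (159) |

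With Table 1's lambda SD of 16.5 instead of 17, at ρ 0.7: two-sided 70% (191 pairs); one-sided 80% (exactly 150 pairs).

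**3. Log scale.** This assumes lognormal data, the same CV before and after, and ρ on the log scale. Log-SD = √ln(1 + CV²): 1.047 for kappa (CV 72/51.0) and 1.254 for lambda (CV 17/8.7). Difference = −ln 0.7 = 0.357. Two-sided 5%, 150 pairs:

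| ρ | Kappa | Lambda |
|---|---|---|
| 0.7 | over 99.9% (N for 80%: 43) | 99% (61) |
| 0.5 | 99% | 93% |
| 0.3 | 94% | 83% |

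**4. Missing follow-up.** The plan gives no rate. If 20% lacked a month-3 sample (assumption), 120 pairs at ρ 0.7, two-sided, would give 85% and 58% on the raw scale, and over 99% and 98% on the log scale.

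**The case against.** The strongest reply is that this is a slip of wording over a sound calculation. The hypothesis is directional, and a one-sided paired t-test on lambda with Table 1's SD of 16.5 and ρ = 0.7 needs exactly 150 pairs and has 80.1% power. That may well be where N came from. But the plan states neither one-sidedness nor lambda as the basis, and the SD it does write, 17, needs 159 pairs and gives 78% at 150. If this was the calculation, it has to be written down.

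It is also fair to say that the 80% is underspecified rather than false in every reading, since no null is given. A null of 0.56 or 0.80 would rescue the number, but no aim asks whether a correlation differs from either value. Correlations are planned, but as estimates and in the exploratory aim; they are not the hypothesis.

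Three limits on the recomputation stand:

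- The raw-scale figures assume equal SD before and after. If the SD also fell by 30%, power at ρ = 0.7, two-sided, would be 95% and 74%.
- The Methodology section says the light-chain:creatinine ratios will be analysed. From the heavily rounded Table 1 ratios (kappa 0.04 ± 0.03, lambda 0.006 ± 0.013), the same raw-scale method gives over 99.9% and about 59%.
- The means and SDs come from a cohort with "use of Ace Inh and/or ARB class of drugs by 75% of the subjects in groups II and III", so off-drug values may differ.

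Finally, this is a pilot collecting preliminary data. That limits the consequence, but the plan still makes a formal power claim.

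**Conclusion.** The concern holds. The power sentence addresses the wrong quantity for the hypothesis, its 80% is wrong against the ordinary null of zero, and no power is derived for the 30% reduction.

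This does not show that 150 is too few. At the plan's own ρ of 0.7, kappa exceeds 80% on either scale, while lambda falls short on the raw scale if tested two-sided and exceeds 80% on the log scale. Across two-sided tests with ρ between 0.5 and 0.7, lambda power runs from 46% to 99%, depending on choices the section leaves open; at ρ = 0.3 on the raw scale it is 35%. Because the SDs exceed the means, the raw-scale normal calculation is rough and the log scale is a realistic option.

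All these figures rest on group III means and SDs applying to this study's patients and on an assumed pre/post correlation. The 150-pair figures also assume no missing follow-up samples.

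**What to change.** Delete the correlation sentence and the 0.88 rationale, and call 0.7 an assumption. State power for the 30% reduction in each light chain, with the test, sidedness, scale, source of the means and a range of correlations. If the test is two-sided, for example:

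> Power is for a 30% reduction in each light chain, paired t-test, two-sided 5%, 150 complete pairs. Means (51.0 and 8.7 mg/L) and SDs (72 and 17 mg/L) come from group III of our earlier cohort; 75% of groups II and III used Ace Inh/ARB, so off-drug values may differ. The pre/post correlation is unknown. Raw scale, equal SD before and after: kappa 92%, lambda 67% at correlation 0.7; 73% and 46% at 0.5. Log scale (lognormal, same CV): over 99% and 99% at 0.7; 99% and 93% at 0.5.

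If one-sided testing was intended, say so and give those figures (raw scale, correlation 0.7: 96% and 78%). The Statistical analysis section should name the same paired test, and the text should say whether the concentration or the creatinine ratio is the variable powered.

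The cost is protocol wording and a team decision on sidedness, scale and variable. N need not change. The downside is a less favourable stated power for lambda if testing is two-sided on the raw scale.

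### Stepwise selection is planned without a named outcome, candidate list, entry rule or validation, so its false-positive rate is uncontrolled and weak effects will be overstated

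*Combined protocol and SAP*

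**What the plan says.** The regression plan in the Statistical analysis section is brief. After two-sample t-tests and chi-square tests it states "Linear or logistic regression models will be fitted to examine effects of covariates", and then "Stepwise model selection methods will be used to identify for potential risk factors or prognostic variables". Residual analysis follows as the check on model assumptions.

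The section does not say which outcome is modelled, which outcomes would take a linear and which a logistic model, which variables are candidates, or what thresholds govern entry and removal. It mentions no shrinkage, resampling, validation or multiplicity control.

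The pool of possible candidates is wide and not closed:

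- The eligibility criteria and Research Design imply age, sex, diabetes type, eGFR and recorded medications.
- The Statistical analysis section names blood pressure, lipids, UMACR, cystatin C and NGAL.
- The budget adds metabolic and lipid panels.
- The Test Period section leaves room for further blood and urine markers if funds allow.
- The Significance section expects many clinical and biochemical variables.

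On size, the Power and sample size section says "We plan to recruit 150 patients".

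**The concern.** Stepwise selection keeps a variable because its estimate in this sample passed a threshold. The ordinary p-values and confidence intervals from the final model ignore that step, so two things go wrong. Variables with no effect enter at a rate set by how many are tried and how lenient the threshold is. True effects that enter are those whose estimates happened to be large, so their coefficients are biased away from zero unless the effect is strong relative to its standard error. Residual plots can look perfect in both cases.

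At stake is the credibility of any list of risk factors or prognostic variables the study reports. The plan sends its data to posters, publications and grant applications. It labels only the cystatin C and NGAL aim as exploratory, not this analysis.

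**Working it through.** **The plan's own figure.** No sample size, power or error rate is given for the stepwise analysis. The only power statement concerns a correlation of 0.7 at N = 150. Against a null of 0, two-sided, Fisher's z gives n = ((1.960 + 0.842)/atanh 0.7)² + 3 = (2.802/0.867)² + 3 = 13.4, so 14 patients. The stated 150 is not reproduced. That is a separate matter and has no bearing here.

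**Inputs.** N = 150 is from the Power and sample size section. Everything else is an assumption, because the plan is silent: 5 to 30 candidates, threshold 0.05 to 0.15, correlation between candidates 0 or 0.3, standardised slopes 0.15, 0.25 or 0.40, residual SD 1.

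**Chance of at least one spurious predictor, all candidates null.** For k independent candidates and threshold a, P = 1 − (1 − a)^k. For example, 1 − 0.95^10 = 0.401 and 1 − 0.85^10 = 0.803.

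| k | a = 0.05 | a = 0.15 |
|---|---|---|
| 5 | 23% | 56% |
| 10 | 40% | 80% |
| 20 | 64% | 96% |
| 30 | 79% | 99% |

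The chance passes 50% when k > ln 0.5/ln(1 − a). That is 13.5 at 0.05 (14 candidates), 6.6 at 0.10 (7) and 4.3 at 0.15 (5). N does not appear in the formula. Simulated stepwise regression at N = 150 with candidates correlated at 0.3 gives somewhat lower values: 36% (k = 10) and 54% (k = 20) at 0.05, and 74% and 91% at 0.15.

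**Does sample size matter for false selection?** The simulation used forward entry with backward removal, 600 to 2,000 runs per setting, three true predictors among the k candidates, and correlation 0.3. Ranges are over the three slopes.

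| k, threshold | N = 150 | N = 1500 |
|---|---|---|
| 10, 0.05 | 32–37% | 25–28% |
| 20, 0.05 | 55–62% | 54–57% |
| 10, 0.15 | 65–70% | 65–67% |
| 20, 0.15 | 92–93% | 89–92% |

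A tenfold increase in N changes little. At N = 150 the spurious share of the selected variables was 11–43% at 0.05 and 25–61% at 0.15.

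**Overstatement of true effects.** For a single uncorrelated predictor the standard error is about 1/√150 = 0.0816, so at 0.05 an estimate must exceed 1.96 × 0.0816 = 0.160 to be selected. The mean of a selected estimate is b + SE × φ(z)/(1 − Φ(z)), with z = (0.160 − b)/SE.

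- b = 0.15: z = 0.123, so 0.15 + 0.0816 × 0.396/0.451 = 0.222, a factor of 1.48.
- b = 0.25: z = −1.10, so 0.25 + 0.0816 × 0.217/0.865 = 0.270, a factor of 1.08.
- b = 0.40: z = −2.94, a factor of 1.00.

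The same formula at threshold 0.15 (cut-off 1.44 × 0.0816 = 0.1175) gives 0.196, a factor of 1.31, for b = 0.15. The simulation with candidates correlated at 0.3 gives larger factors, over both thresholds:

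| True slope | N = 150 | N = 1500 |
|---|---|---|
| 0.15 | 1.46–1.69 | 1.00–1.01 |
| 0.25 | 1.10–1.19 | 1.00 |
| 0.40 | 1.00–1.01 | 1.00 |

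Overstatement is therefore the part that depends on N.

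**Several outcomes.** The plan has kappa, lambda, their creatinine ratios and UMACR available as outcomes, but does not say how many would be modelled. Two independent outcomes with 10 null candidates each at 0.05 would give 1 − 0.95^20 = 64%, against 40% for one.

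**The case against.** The plan speaks only of potential factors, which is screening language. The study is meant to supply preliminary data, and a biostatistician is to be consulted on analysis and interpretation. Both main aims concern urinary free light chains and UMACR before and after three months of treatment, and neither depends on stepwise selection. All of this stands and limits the weight of the point. It does not remove the defect: the method is stated, no safeguard is, and a consultation with someone not yet named does not replace the written method.

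A reader might infer more than the documents support:

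- *That the procedure will usually return spurious predictors.* With 5 or 10 null candidates at 0.05 the chance is 23% or 40%. It passes one half only with more candidates or a looser threshold, and the plan gives neither number.
- *That 150 patients is the cause of false selection.* The rates at N = 1500 are similar.
- *That every reported effect size is invalid.* Strong effects are barely changed. Marked overstatement is confined to weak ones.
- *That results will be reported as if the model had been fixed in advance, or that stepwise coefficients will set the design of the longitudinal study.* The plan does not say how these results will be reported. It bases the later study on comparing free light chains with UMACR.

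**Conclusion.** The concern holds as a defect in a secondary analysis. The plan commits to data-driven selection with nothing fixed in advance and no check that addresses selection. The chance of at least one spurious predictor, if all candidates are null, could be anywhere from about 23% to 99% over the assumed range of 5 to 30 candidates and thresholds of 0.05 to 0.15.

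The overstatement of 1.5 to 1.7 fold for slopes near 0.15 assumes linear models, 150 analysed patients and candidates correlated at 0.3. With uncorrelated candidates it is about 1.3 to 1.5 fold. Dropout, for which the sample size section makes no allowance, would make it somewhat larger. Logistic models were not simulated; for them the number of events, which the plan does not give, is the limiting size. The before/after comparison is unaffected.

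**What to change.** Replace the stepwise sentence with one pre-specified linear model:

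- **Outcome:** named in advance, for example the log post-treatment urinary free light chain:creatinine ratio.
- **Covariates:** a short list fixed before the data are seen, for example the baseline value of the marker, age, sex, eGFR, blood pressure and diabetes type.
- **Reporting:** all coefficients with 95% CIs, whether or not they reach significance.

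If a data-driven search is still wanted, list its candidates, use penalised regression with bootstrap optimism correction, and label the result hypothesis-generating.

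The particular outcome and covariates are for the investigators to choose; what matters is that they are fixed beforehand. The cost is a few lines of text, with no added patients or visits. The model needs the baseline and post-treatment light chain values that the aims already require. The budget appears to price one such test per patient, which has to be reconciled with the aims in any case. The downside is that covariates outside the list are examined only descriptively.
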